Official Title of the Study:

Improving Voluntary Engagement for PTSD Treatment among Service Members

Date:

January 30, 2018

NCT ID:

Not yet assigned

STUDY PROTOCOL

Objectives

This study will develop and test a brief motivational enhancement intervention for active duty Army and Air Force personnel who are experiencing symptoms of PTSD and who are not currently in treatment. The intervention is designed to prompt: (1) a willingness to participate voluntarily in a self-appraisal of PTSD symptoms, (2) increased perceptions of PTSD treatment effectiveness, (3) reduced perceptions of stigma associated with mental healthcare, (4) engagement in PTSD treatment or other self-help programs, and (5) reductions in PTSD symptoms. The proposed study will test the efficacy of this intervention against a comparison condition of treatment-as-usual – written referrals to treatment options.

Hypotheses

H1: Individuals receiving the MET intervention will report more PTSD treatment engagement at follow-up relative to participants in the comparison condition.

H2: Individuals receiving the MET intervention will experience fewer PTSD symptoms at follow-up relative to participants in the comparison condition.

H3: The effect of the intervention on PTSD symptoms will be mediated by PTSD treatment engagement.

H4: The impact of the intervention on PTSD treatment engagement at the 6-month follow-up will be mediated by decreased perceived stigma associated with PTSD treatment and increased perceived effectiveness of treatment for PTSD, both of which will be targeted by the MET intervention.

Methods

Design. In a randomized controlled trial, the experimental (MET) and control (TAU) interventions will be compared. Participants (N = 200) will be randomly assigned to receive the MET condition or TAU. Both interventions will be preceded by telephone-administered screening and baseline assessments. Telephone administered follow-up assessments at 1 week, 3, and 6 months will assess post-intervention change in pertinent intentions, treatment participation, behaviors, symptoms, and perceptions of stigma and treatment effectiveness.

Study Population. Study participants will be active duty Army and Air Force personnel stationed at Joint Base Lewis-McCord (JBLM). JBLM has a population of active duty personnel of approximately 46,496 ([name], 2014). The demographic characteristics of the JBLM sample are expected to mirror demographic characteristics of Army and Air Force personnel in general. Participant selection will be equitable – inclusion/exclusion criteria are minimal and there are no limitations on age, race, ethnicity or sex included in the study.

Eligibility Criteria. Eligibility for enrollment and random assignment to the two conditions will be based on the following criteria: 1) current PTSD, 2) not currently being treated (counseling and/or medication) for PTSD, and 3) currently serving in the Army or Air Force. Exclusion criteria include: 1) non-fluency in English, 2) evidence of psychosis, 3) pending deployment that would preclude completion of follow-ups. Callers who do not meet eligibility criteria, but who are concerned about PTSD symptoms, will be provided the opportunity to speak with a counselor and to discuss their thoughts and concerns surrounding their symptoms. Counselors will provide

a 15-45 minute Motivational Interviewing (MI) session focused on their PTSD symptoms, and an exploration of options for ongoing support. Referrals to local treatment agencies and self-help options will also be available to the ineligible caller.

Relevant Scientific Background

Posttraumatic Stress (PTS) is associated with serious health and psychological effects. The health and well-being of military personnel, and consequently the capacity for optimal functioning of military units, are compromised by PTS. Rates of PTS are high among military personnel with post-deployment rates ranging from 5-20% (Hoge et al., 2004). Untreated PTS is associated with high rates of suicide, medical services utilization, relationship impairment, legal difficulties, decreased worker productivity, and decreased military readiness (Hoge et al., 2006; Hoge et al., 2007; Kline et al., 2010; Tanielian et al., 2008).

Interventions can lead to long-lasting reductions in PTS symptom severity. There are multiple effective interventions for PTS with a high degree of research evidence supporting their efficacy (Bisson & Andrew, 2005; Bradley et al., 2005), including trauma-focused cognitive behavioral therapies (e.g., Prolonged Exposure, Cognitive Processing Therapy and Eye movement Desensitization and Reprocessing) and pharmacotherapies (e.g., SSRIs) (Forbes et al., 2010; VA/DoD, 2004). However, while treatment can be effective, individuals may not seek treatment. Drop-out and medication noncompliance are common. Despite treatment options, the majority of military personnel affected by PTS do not present for treatment (Steenkamp & Litz, 2013). For example, less than 10% received the recommended exposure to PTSD treatment by attending 9 or more VA mental health treatment sessions in 15 weeks or less during the first year of PTSD diagnosis (Seal et al., 2010). For medications, on average, approximately 30% of those prescribed medications for PTSD also drop out (Ravindran & Stein, 2009).

Military personnel encounter more real and perceived barriers to seeking treatment than people in the general community, such as stigma, fear of a diagnosis appearing on one's service record, the perception that diagnosis would reflect negatively on one's unit, work interference, geographical distance, and the belief that treatment is ineffective (Gould et al., 2007).

A brief, telephone-delivered motivational enhancement intervention (MET) called a "check-up," has shown promise in promoting self-initiated behavior change as well as voluntary treatment entry, enhanced retention, and more successful outcomes for soldiers with substance use disorders (Walker et al., 2017). Why MET for PTS? Efficacious options for treatment are available for PTS and the military has invested considerable resources into scaling up access to care. However, rates of self-referral and retention are low among active duty military. Given the availability of effective treatments contrasted with the low rates of military personnel who present and complete treatment, figuring out how to connect individuals with PTSD symptoms into treatment and then helping them to stay engaged is a high priority. Adapting the "check-up" for application with military personnel experiencing PTS symptoms is warranted for three key reasons: (1) it has the potential of overcoming barriers to treatment seeking, i.e., stigma and apprehension of a negative impact on one's military career; (2) it has the potential of attracting voluntary participation; and (3) protocols for disseminating this low-cost intervention for use with deployed military can readily be developed and evaluated.

Summary. Adapting the “check-up” variant of motivational enhancement therapy for application with military personnel is warranted for three key reasons: (1) permitting anonymous participation through a telephone delivered intervention has the potential of overcoming a major barrier to treatment-seeking among those who are concerned about their behavior, i.e., stigma and apprehension that being identified as having PTSD will negatively impact one’s military career and providing information about efficacy; (2) the nature of the check-up intervention as an opportunity to take stock of one’s PTSD experiences without being pressured to change, and the use of an empathic counseling style in its delivery, have the potential of attracting voluntary participation among individuals who would otherwise be deterred by concerns of being judged negatively and of being pressured to enter treatment; and (3) if the check-up is efficacious in voluntarily recruiting untreated service personnel with PTSD and promoting treatment engagement, support group participation, or self-initiated behavior change, protocols for disseminating this low cost and brief intervention for use with deployed military can readily be developed and evaluated.

STATISTICAL ANALYSIS PLAN

The primary data assessed at baseline and follow-up points via interviews and questionnaires will be entered into SPSS for Windows data entry (DE) files. Out-of-range values and skip rules will be built into DE files to facilitate data entry. All data will be double entered into the DE files by two different people to ensure accuracy.

Following data cleaning, initial analyses will focus on assessing the psychometric properties of the assessments and constructing scale scores where appropriate. Univariate and bivariate descriptive analyses will be performed to examine distributions of and correlations among key study variables. In the event that variables show non-normal distributions (which could lead to violation of regression model assumptions), we will consider using generalized forms of models (e.g., Poisson or negative binomial count regression) or transformation of the outcome variable(s) of interest.

Hypotheses 1 and 2 evaluate whether MET participants will report more treatment engagement and fewer PTSD symptoms at follow-up than TAU participants. This study will have 4 repeated measures from baseline to 6 months follow-up yielding up to 800 observations. Given the nesting of observations within individuals, we will run linear mixed (also known as hierarchical linear or multilevel) models (Diggle, Heagerty, Liang, & Zeger, 2002) to test study hypotheses. Measures of PTSD symptoms (CAPS) and treatment engagement (TAQ) will be analyzed as outcomes in separate models. Fixed effects will include indicator variables for time (1-week, 3-months, 6-months) with baseline as the reference, intervention condition, and the interaction between time point and condition. The following represents the basic model:

$$\text{Level 1: } Y_{ti} = \pi_0 + \pi_1(\text{Time1wk})_i + \pi_2(\text{Time3m})_i + \pi_3(\text{Time6m})_i$$

$$\text{Level 2: } \pi_0 = \beta_{00} + \beta_{01}(\text{Treat}) + r_{00i}$$

$$\pi_1 = \beta_{10} + \beta_{11}(\text{Treat}) + r_{10i}$$

$$\pi_2 = \beta_{20} + \beta_{21}(\text{Treat}) + r_{20i}$$

$$\pi_3 = \beta_{30} + \beta_{31}(\text{Treat}) + r_{30i}$$

where Y_{ti} represents the continuous outcome for individual i at time t ; Time1wk , Time3m , and Time6m are the indicator variables for study time points where baseline is the reference; Treat represents the variable for intervention condition; and r_{00i} through r_{30i} represent random subject specific deviations from the corresponding overall intercept or slope. Of particular interest are the coefficients β_{11} , β_{21} , and β_{31} , which describe the cross-level interactions between intervention condition and time. For analyses of PTSD symptom score as the outcome, we expect that these interaction terms will be negative and statistically significant suggesting that PTSD symptoms are lower at follow-up visits among those randomized to the MET intervention compared to those in the control group. We will consider inclusion of additional covariates such as gender, social support, and trauma severity to improve precision of estimates. We will also explore modeling time as a continuous measure to assess treatment differences on slopes over time. Similar mixed effects models will be used to test effects of the intervention on stigma/barriers to treatment (PSBCPP) and treatment expectancies (CEQ) as well as secondary outcomes such as anxiety and depression symptoms.

For analyses involving multiple outcomes, we will guard against Type I error by adjusting criteria for statistical significance for multiple testing (e.g., using global tests that test for an overall difference across outcomes while accounting for their inter-correlation or Benjamini-Hochberg corrections for the false discovery rate) where appropriate.

For hypothesis 3, we will test whether the effect of the intervention on PTSD symptoms will be mediated by PTSD treatment engagement. For hypothesis 4, we will test whether effects of the intervention on treatment engagement are mediated through stigma and treatment expectancies. We will evaluate the effect of the intervention on change in the outcome (e.g., PTSD symptoms) both before and after controlling for the putative mediator(s) (e.g., treatment engagement) using the method described by Krull and MacKinnon (1999; 2001). Reduction in the percentage of variance accounted for by the interaction effect after controlling for the mediator(s) will inform the degree to which the effect is mediated.

Missing Data and Attrition

Based on retention rates in our ongoing clinical trial, we expect no more than 20% attrition by 6-month follow-up in this proposed study. Linear mixed models provide unbiased estimates in the presence of missing data as long as it can be considered ignorable (Atkins, 2005). Missing data are ignorable if they are either missing completely at random or related to variables in the analysis, including earlier time points of the outcome (Graham, 2009). Little efficiency is lost in linear mixed models with 10%-20% missing data. As a safe-guard against the possibility of nonignorable missing data, we will use pattern-mixture models for non-ignorable missing data that directly assess sensitivity of findings to the presence of missing data (Atkins, 2005).

Sample Size and Power

This study was powered to detect differences in PTSD symptoms between the intervention condition and control group over time. We used a simulation-based approach to estimate power for this study (Gelman & Hill, 2007). Using R statistical software, 1,000 datasets were generated based on the linear mixed model equation provided in the Analysis Plan. Estimates for model parameters for standardized PTSD scores (e.g., baseline intercept, slopes for time, distribution of random effects) were guided by preliminary data from our ongoing clinical trial. We also specified missingness of 13% and 19% at 3- and 6-month follow-up, respectively, according to missing data patterns in the ongoing trial. The model was fit for each of the 1000 datasets. A number of simulation runs were conducted varying the size of the treatment effects and fixing the sample size to 200. The percentage of datasets where the treatment-by-time interactions were statistically significant provides an estimate of power. Based on these simulations, this study should have $>.8$ power to detect effect sizes of $.36$ or greater at any given follow-up visit. An effect size of $.36$ is at the lower end of the range found in the extant literature on treatment for PTSD in military samples. The conservative estimate seems appropriate given the non-treatment seeking nature of the population yet is still clinically meaningful. For instance, a $.35$ effect size translates to a mean difference of approximately 6 points between conditions on the PTSD symptom checklist based on data collected in our current ongoing trial.

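### The H2 model estimates a baseline arm difference that randomisation sets to zero; a common baseline mean tests the same contrast with variance about 0–18% lower, depending on unstated correlations and SDs

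*Combined protocol and SAP*

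**What the plan says.** In the Statistical Analysis Plan (Hypotheses 1 and 2), baseline is one of four outcome occasions. The fixed effects are "indicator variables for time (1-week, 3-months, 6-months) with baseline as the reference, intervention condition, and the interaction between time point and condition". The Level 2 intercept carries a condition coefficient, beta_01, so baseline means may differ by arm. Inference rests on beta_11, beta_21 and beta_31, "which describe the cross-level interactions between intervention condition and time"; each is a between-arm difference in change from baseline.

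The random terms are "random subject specific deviations from the corresponding overall intercept or slope". Whether they may correlate is not stated. On precision, the plan says: "We will consider inclusion of additional covariates such as gender, social support, and trauma severity to improve precision of estimates". It does not mention adjusting for, or constraining, the baseline value of the outcome.

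Under Methods, Design: "Both interventions will be preceded by telephone-administered screening and baseline assessments". Under Eligibility Criteria: "Eligibility for enrollment and random assignment to the two conditions will be based on the following criteria: 1) current PTSD". Under Sample Size and Power, the simulation used the planned model: "The percentage of datasets where the treatment-by-time interactions were statistically significant provides an estimate of power". The mediation analyses for H3 and H4 look at "the effect of the intervention on change in the outcome (e.g., PTSD symptoms) both before and after controlling" for the mediator.

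**The concern.** H2 is about symptoms at follow-up. In a randomised trial with a pre-intervention baseline, the arms share one baseline population mean, so beta_01 has expectation zero and the interactions estimate the follow-up difference without bias. But they do so by subtracting the whole observed baseline difference, which is pure noise, with a coefficient of 1. A model with a common baseline mean subtracts only the part that the baseline predicts. With a correctly specified covariance it is never less precise, apart from a small cost of estimating that covariance.

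The sample size is fixed at 200 and the plan is already looking for precision from optional covariates. The baseline outcome score is collected anyway and is left out of that search. At stake is the width of the CAPS intervals, not the validity of the test.

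**Working it through.** **Inputs from the documents.** N = 200; power above .8 for a standardised effect of .36 at any follow-up visit; missingness 13% at 3 months and 19% at 6 months (Sample Size and Power).

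**Not given, so assumed.** 1:1 allocation (100 per arm), two-sided alpha .05, no missingness at 1 week, monotone dropout, constant within-person correlation rho. Let s be follow-up SD divided by baseline SD.

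**Formulas for one follow-up visit, n per arm, baseline SD = 1.**
- Free baseline difference (as planned): variance = (2/n)(1 + s² − 2·rho·s).
- Common baseline mean: variance = (2/n)·s²·(1 − rho²).
- Relative reduction = (1 − rho·s)² / (1 + s² − 2·rho·s). This is (1 − rho)/2 when s = 1, and zero when rho·s = 1.

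**Plan's power figure.** It cannot be reproduced outright, because rho, the SDs and alpha are missing. It can be used to find the rho it implies. With s = 1 and 81 per arm at 6 months, the one-visit formula gives power .63 at rho .5, .73 at .6, .78 at .65 and .84 at .7. Power .80 needs rho of about .67, where the reduction is about (1 − .666)/2 = 16.7%.

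**All four visits.** Generalised least squares with the stated missingness also uses the earlier visits of those who drop out. Planned 6-month power of exactly .80 then needs rho = .644 (s = 1).
- 1 week, nobody missing: (1 − .644)/2 = 17.8%. At 3 and 6 months the reductions are 16.1% and 15.4%.
- Planned 6-month standard error: .36/(1.96 + .84) = .1285. With a common baseline: .1285 × √(1 − .154) = .1182, an interval 8.0% narrower.
- Power: .36/.1182 − 1.96 = 1.09, which gives .86.
- Equivalent sample size for this contrast: 200/(1 − .154) = about 236.

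**Higher planned power.** The plan says above .8. If planned 6-month power is .85, .90 or .95 (rho .689, .735, .786; s = 1), the variance falls 13.4%, 11.4% or 9.2%, and power becomes .90, .93 or .97.

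**Unequal SDs.** Entry requires current PTSD, which may make the follow-up SD larger than the baseline SD. Ranges show the effect of .36 read in baseline or follow-up SD units.

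| s | rho at planned power .80 | 6-month variance fall | 6-month power | Fall at planned power .90 |
|---|---|---|---|---|
| 1.0 | .644 | 15.4% | .86 | 11.4% |
| 1.1 | .685 or .617 | 7–10% | .83–.84 | 4–6% |
| 1.2 | .726 or .597 | 2–7% | .81–.83 | 0.3–3% |
| 1.3 | .766 or .583 | 0–4% | .80–.82 | about 1% |

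The nil entry follows from the formula: 1 − .766 × 1.3 = .004. With s = 0.9 the 6-month fall at planned power .80 is about 22–25%.

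**Correlation that decays with time.** With s = 1 and 6-month power still .80, a decaying pattern gave falls of 7.5%, 12.6% and 15.1% at the three visits.

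**Downside.** In simulations with an estimated unstructured covariance (6,000 datasets per setting), bias of the common-baseline estimate was at most .003. Null rejection was .046–.060, against .046–.058 for the planned model. In the zero-gain case (s = 1.3, rho .766) variance rose 0.3–0.8%. With a compound-symmetry working model at s = 1.3 and rho .644–.70, it rose 1–5%.

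**The case against.** The best case for leaving the plan alone is that nothing in it is wrong. The interactions are valid for H2, and the power simulation used this same model and met its target. The gain may also be small: the entry criterion points towards s above 1, where it shrinks and can vanish. The 18% is the 1-week figure under equal SDs, constant correlation and power of exactly .80. The documents also say that baseline precedes the interventions, not that it precedes allocation or knowledge of the arm.

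Most of this stands as a limit on the claim. The range of 0–18% is not a mathematical bound. It is exceeded if follow-up SDs are below the baseline SD. It is also exceeded at 1 week if a near-perfect correlation there goes with an SD ratio well above 1, a case where planned power is already essentially 1. That gains can be larger does not weaken the point. The timing of baseline is a reasonable inference that the plan should turn into a statement, and the change depends on it. The linear-model figures also do not carry over directly if the plan's fallback to count models or transformation is used.

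None of this removes the reason to change: the cost is a few lines, the worst case with an unstructured covariance is a variance increase below 1%, and no new data are required.

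**Conclusion.** The concern holds as an efficiency point. The plan estimates a baseline arm difference that is zero in expectation under randomisation, and so gives up precision on CAPS. Under the assumptions above, with the follow-up SD at or above the baseline SD and correlations tied to the plan's own power statement, the variance of the visit contrasts could be about 0–18% lower. At 6 months, planned power of .80 would become .80 to .86. The stated power remains correct for the planned model, and no result would be biased.

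The same logic applies to stigma, expectancy, anxiety and depression where these are measured at baseline, but the documents give nothing from which to size the gain. It does not extend to treatment engagement (TAQ, H1).

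**What to change.** For CAPS, and for PSBCPP, CEQ, anxiety and depression where measured at baseline:

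- Prespecify a common baseline mean across arms: drop the condition main effect (beta_01 = 0) and keep the three condition-by-visit terms. Each coefficient is then the between-arm difference at that visit.
- Name an unstructured covariance across the four visits. If the four printed random deviations may correlate freely, the planned model already implies one; the plan should say so.
- State that baseline is collected before the assigned arm is known.
- Reword the H3 and H4 mediation paragraph, which speaks of change in the outcome and of the interaction effect, to match these terms.
- Leave the TAQ model (H1) outside this change.

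The cost is SAP wording only. The power statement can stand for the planned model, or the simulation can be re-run with the term dropped. The change should be made before unblinded data are seen, since adopting it after a baseline imbalance has been observed would invite criticism.

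### Does the basic mixed model, with four random effects on four visits and no stated covariance or fallback, need to be respecified?

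*Combined protocol and SAP*

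**What the plan says.** The SAP paragraph on Hypotheses 1 and 2 sets out the data: "This study will have 4 repeated measures from baseline to 6 months follow-up yielding up to 800 observations". Level 1 has an intercept and three visit indicators with baseline as reference, and no error term is printed. Level 2 adds a participant-specific term to each of the four coefficients. The SAP says these terms "represent random subject specific deviations from the corresponding overall intercept or slope" and gives nothing on their variances or correlations. The coefficients of interest are the three treatment-by-visit interactions, β11, β21 and β31.

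The same form serves both main outcomes: "Measures of PTSD symptoms (CAPS) and treatment engagement (TAQ) will be analyzed as outcomes in separate models". The opening SAP paragraphs contain one modelling contingency, which begins "In the event that variables show non-normal distributions" and leads to count models or a transformation. A continuous-time version is offered as exploratory. Neither is a fallback for the covariance.

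Under Sample Size and Power, "1,000 datasets were generated based on the linear mixed model equation provided in the Analysis Plan". That section adds: "Estimates for model parameters for standardized PTSD scores (e.g., baseline intercept, slopes for time, distribution of random effects) were guided by preliminary data". Dropout is also given: "We also specified missingness of 13% and 19% at 3- and 6-month follow-up, respectively". The section then reports that the model was fitted to every simulated dataset, without naming the covariance used.

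**The concern.** A linear mixed model usually carries a residual. With four random effects on four visits there is nothing left for a residual to explain, so an analyst who adds one to freely correlated effects has a model whose variance components cannot be separated. Software may refuse it or stop without converging. The plan says nothing about what follows, so a simpler covariance could be picked after the data are seen.

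That choice can matter. A random intercept, or independent random effects, forces the same covariance on every pair of visits. If correlations fade with time, the model-based standard error is too small at 6 months and too large at 1 week, and those are tests of H1 and H2.

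The engagement model raises a further worry. Entrants must be "not currently being treated (counseling and/or medication) for PTSD", so baseline spread on the TAQ may be small. A random-intercept model would force that small variance to equal the follow-up variance.

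**Working it through.** **Inputs.** From the documents: N = 200, four visits, 13% and 19% missing at 3 and 6 months, effect size .36, power above .8. Assumed, because not stated: 1:1 allocation, two-sided 5% tests, monotone random dropout (81% complete, 6% missing 6 months only, 13% missing 3 and 6 months), visit variances of 1, and all correlations.

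**1. Is the model identified?** Let Z be the 4x4 matrix of the intercept and three visit indicators; its determinant is 1. The within-person covariance is V = ZGZ′ + σ²I, with 4 × 5 / 2 = 10 distinct elements.

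| Reading | Parameters | Rank | Identified |
|---|---|---|---|
| Correlated effects, no residual (as printed) | 10 | 10 | yes |
| Independent effects plus residual | 4 + 1 = 5 | 5 | yes |
| Random intercept plus residual | 2 | 2 | yes |
| Correlated effects plus residual | 10 + 1 = 11 | 10 | no |

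Because Z is invertible, the first row can reproduce any V. It is the unstructured model.

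**2. What does the unidentified reading do to the tests?** Take V with variance 1 and correlation .6. For any admissible σ², set G = Z⁻¹(V − σ²I)Z⁻ᵀ. Residual variances of 0, .1, .2, .3 and .39 each give a valid G and exactly the same V. At baseline, for example, σ² = .2 goes with an intercept variance of .8, and .8 + .2 = 1. The interaction estimates and standard errors depend on the data through V only, so they do not move. Just the split between G and the residual is arbitrary.

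**3. Would a failed fit be noticed?** There are 200 × 4 = 800 random effects and, with the stated missingness, 200 + 200 + 174 + 162 = 736 expected observations. A refusal on that count is visible. Removing the residual cures it and returns the printed equation.

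**4. Can the unstructured model be fitted?** In REML simulations with 10,000 trials per setting, every unstructured fit converged. Its 6-month type I error was .047 (constant correlation .65), .048 (lag correlations .75/.70/.65), .056 (.80/.65/.50) and .050 in an assumed TAQ-like case (SDs .3/.5/.8/1, baseline correlation .2, follow-up correlation .6). The Monte Carlo standard error is about .002.

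**5. The stated power.** With generalised least squares and constant correlation ρ, power for .36 at 1 week, 3 months and 6 months is .72/.68/.66 at ρ = .5 and .86/.83/.81 at ρ = .65. At 1 week, for example, the standard error is √(4(1 − ρ)/100) = √(4 × .35/100) = .118. Power above .8 at every visit is therefore attainable, and under constant correlation it needs ρ of about .65 or more. The figure cannot be confirmed exactly without the sponsor's variance components.

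**6. Size of the error if someone did simplify.** Type I error is P(|t₁₉₈| > 1.972 × model SE / true SE), with the model SE taken at the limiting fit of the simpler covariance. At 6 months:

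| Lag correlations (assumed) | Unstructured power for .36 | Independent effects plus residual | Random intercept only |
|---|---|---|---|
| .65 constant | .803 | .050 | .050 |
| .75/.70/.65 | .807 | .069 | .078 |
| .85/.75/.65 | .814 | .096 | .124 |
| .80/.65/.50 | .669 | .100 | .130 |

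Power here uses the t distribution on 198 df, which is why .803 sits slightly below the .81 in step 5. For the third row, with independent effects, 1.972 × .1077/.1268 = 1.675, which gives .096. With a random intercept, 1.972 × .0993/.1268 = 1.544, which gives .124. The last row does not fit the plan's claim of power above .8. In that row the 1-week test errs the other way, at .028 and .018.

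**7. TAQ.** In the TAQ-like case a random intercept alone gives .138 at 6 months and .005 at 1 week. The printed covariance holds .050 at both visits (simulated).

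**The case for a change.** The best case for a change is that the plan fixes neither the covariance nor a fallback for its main tests, and that the choice has consequences. Some assumed correlations that agree with the stated 6-month power still take its 6-month type I error to .096 or .124 under a simplified model with ordinary standard errors. The sponsor seems to hold preliminary values that would show which case applies, and the power simulation must have used some covariance that is not reported. One added sentence would cost almost nothing.

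Much of this stands. The covariance is unstated, the distortion is possible, and the power figure cannot be reproduced exactly. But the sentence would only write down the model already printed. The distortion comes from a simplification that the plan does not propose, made without robust standard errors. The one statement on feasibility, that the model was fitted to every simulated dataset, points away from a fit that cannot be obtained, although it does not say which covariance was used or that every fit converged.

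The TAQ argument is weaker. The instrument's content is not described, so a small baseline spread is conjecture. A scale with many zeros would in any case be handled through the SAP's provision for non-normal outcomes.

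**Conclusion.** No change follows. The omission is one of detail, and a competent analyst fills it with the unstructured covariance that the equation already implies. Two of the three ways of reading the four random effects are identified, and the third leaves β11, β21, β31 and their standard errors as they were. The algebra needs no assumed values.

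The size of a possible error rests entirely on assumed correlations. Where these agree with the stated 6-month power, an unplanned simplification with model-based standard errors gives a 6-month type I error from .050 (no decay) to .124 (lag correlations .85/.75/.65, random intercept only). This would become a real fault if the analysis used a simplified covariance with model-based standard errors. The plan as written does not say that it will.
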